8.10. Electrocardiography

Electrocardiography was not collected for this study.

8.11. Oropharyngeal Examinations

Oropharyngeal examinations for visual evidence of oral candidiasis will be conducted at the scheduled investigational center visits. This will be evaluated by obtaining and analyzing a swab of the suspect area. Any occurrence of oropharyngeal candidiasis that is confirmed by culture during the study will be reported as an adverse event.

The number and percentage of patients with clinical/visual evidence of oral candidiasis will be tabulated for each treatment group at each visit. In addition, the number and percentage of patients with a positive swab will be tabulated for each treatment group at each visit.

A listing of all visual evidence of oral candidiasis will be provided.

8.12. Concomitant Medications or Therapies

Concomitant therapies and medications, including medications that are taken on an as needed basis and occasional therapies, will be monitored during the study. Details of prohibited medications may be found in Section 5.7 and Appendix H of the FSS-AS-30003 study protocol. All concomitant medications will be coded using the WHO Drug.

The incidence of concomitant therapies and medications will be summarized using descriptive statistics by therapeutic class category and preferred term. Patients are counted only once in each therapeutic class, and only once in each preferred term category. Concomitant therapies and medications will include all medications taken while the patient is being treated with IMP as defined in the FSS-AS-30003 study protocol. In addition, a separate summary table will be provided for patients who discontinue IMP but stay in the study.

9. TOLERABILITY VARIABLES AND ANALYSIS

Tolerability will be assessed via other endpoints.

10. STATISTICAL SOFTWARE

All data listings, summaries, and statistical analyses will be generated using SAS[®] version 9.4 or later.

11. CHANGES TO ANALYSES SPECIFIED IN THE STUDY PROTOCOL

There is no change to the analyses specified in the FSS-AS-30003 clinical study protocol. Only one clarification to the PP analysis set has been made.

Table 12: Changes to the Statistical Analysis Plan

SAP Section	Protocol Description	SAP Change	Rationale
3.3	
The per-protocol (PP) analysis set is a subset of the ITT analysis set including only patients without major protocol violations and who have >80% compliance to the IMP over the entire treatment period. Treatment compliance during the study will be assessed based on data collected in the IMP dose counter. In the event the IMP isn't returned by a patient or a dose counter is broken, treatment compliance will be assessed based on the patient's diary. Major protocol violations will be determined before unblinding. Note that since the use of incorrect IMP will be considered a major protocol violation, for treatment assignment in the PP analysis set, "as randomized" will coincide with "as treated."
	
The per-protocol (PP) analysis set is a subset of the ITT analysis set including only patients without protocol violations that could have an effect on the primary outcome and who have greater than or equal to 80% compliance to the IMP over the entire treatment period. The compliance rate calculation is detailed in section 8.3.
 
PP analysis set will be determined before unblinding at the Statistical Data Review (SDR) meeting and documented in the SDR meeting minutes. Note that since the use of incorrect IMP will be considered a protocol violation and will not be included in the PP analysis set, for treatment assignment in the PP analysis set, "as randomized" will coincide with "as treated".
	
This change was made so that the language is consistent with SOP GBP-RD-312

APPENDIX A. MULTIPLE IMPUTATION STEPS FOR PRIMARY ENDPOINTS

The following represents an outline of the planned methodology for the multiple imputation (MI) procedure for the primary analyses. Minor deviations from this outline will be addressed in the CSR. In the situation that more significant updates are warranted, changes will be addressed in a SAP amendment to be finalized prior to database lock.

Change from Baseline in Weekly Average of the Percent Predicted Trough Morning FEV₁ at Week 12:

Multiple imputation (MI) method will be applied to impute the weekly missing data that are caused by early discontinuation from the study or from IMP (regardless of availability of retrieved dropout data). The data will be processed by the following steps:

1. For all patients who prematurely discontinue from IMP, regardless of assigned treatment arm, imputation will be based on data from the placebo-treated patients (eg, reference-based imputation).
2. For patients who completed the treatment period but with clinically and physiologically implausible data (eg, percent predicted FEV₁ values postrandomization are $\geq 200\%$), imputation will be based on data from patients treated with the same treatment.
3. Assume patients with arbitrary missing data patterns, the fully conditional specification statement will be used to impute by using regression with treatment arm and percent predicted FEV₁ measurements from previous weeks as explanatory variables.

```
proc mi data=outmi_mono seed=56789 nimpute=10 out=outmi;
    class sex therapy center trt;
    fcs nbiter=50 reg(wk1= &covlist / details);
    fcs nbiter=50 reg(wk2= &covlist wk1 / details);
    fcs nbiter=50 reg(wk3= &covlist wk1 wk2 / details);
    fcs nbiter=50 reg(wk4= &covlist wk1 wk2 wk3 / details);
    fcs nbiter=50 reg(wk5= &covlist wk1 wk2 wk3
        wk4 / details);
    fcs nbiter=50 reg(wk6= &covlist wk1 wk2 wk3
        wk4 wk5 / details);
    fcs nbiter=50 reg(wk7= &covlist wk1 wk2 wk3
        wk4 wk5 wk6 / details);
    fcs nbiter=50 reg(wk8= &covlist wk1 wk2 wk3
        wk4 wk5 wk6 wk7 / details);
    fcs nbiter=50 reg(wk9= &covlist wk1 wk2 wk3
        wk4 wk5 wk6 wk7 wk8 / details);
```

```

fcs nbiter=50 reg(wk10= &covlist wk1 wk2 wk3
                 wk4 wk5 wk6 wk7 wk8 wk9 / details);
fcs nbiter=50 reg(wk11= &covlist wk1 wk2 wk3
                 wk4 wk5 wk6 wk7 wk8 wk9 wk10 / details);
fcs nbiter=50 reg(wk12= &covlist wk1 wk2 wk3
                 wk4 wk5 wk6 wk7 wk8 wk9 wk10 wk11 /
                 details);

var trt &covlist wk1 - wk12;

mnar model( wk1 - wk12 / modelobs = (trt = "D"));

run;

```

where: the order of &covlist includes: sex, (pooled) investigational center, previous therapy, base, and age
Note: wk1 - wk12 is the AVAL raw data, change from baseline values should not be used in PROC MI procedure.

- The ANCOVA model will be fitted to the above dataset using the model described in Section 6.2.2.1. The difference will be estimated in adjusted LS means and p-value will be output for each dataset. An example SAS code to the following will be used:

```

proc mixed data=fev_model;
  where week = "week 12";

  class sex center therapy trt;

  model chg= base sex age therapy trt;

  lsmeans trt/diff=CONTROL("Placebo") cl alpha=0.05;

  ods output Estimates=Est LSMeans=lsmeans Diffs=Diffs;

run;

```

where: chg is the change from baseline percent predicted FEV1 value at week 12.

- The results from the ANCOVA model will be combined using the following code:

```

data diff2;
  set diff;

  comparison=trt||' vs '||left(_trt);

run;

proc sort data=diff2;
  by comparison;

```

```
run;
```

6. The SAS[®] procedure PROC MIANALYZE procedure will be used to generate the final LS means for the treatment groups, treatment difference as well as p-values associated with treatment differences. The 95% confidence intervals for the treatment differences will be also calculated. An example of the SAS code will be used:

```
proc mianalyze data=diff2;  
    by comparison;  
    modeleffects estimate;  
    stderr stderr;  
    ods output ParameterEstimates=mianalyzeparm;  
run;
```

Change from Baseline in 1-hour Postdose Percent Predicted Morning FEV₁ at Week 12:

The 1-hour postdose percent predicted morning FEV₁ measurement will be performed at the investigational center at the RV, TV2 (week 1), TV3 (week 2), TV4 (week 4), TV5 (week 8) and TV6 (week 12). The MI method will be applied similarly to impute the 1-hour postdose missing data that are caused by early dropouts from IMP without including retrieve dropout data. Steps 1 to 6 will be repeated similarly.

Sensitivity Analysis: Effectiveness with retrieved dropout data:

In order to evaluate the estimand of the effect of the treatment regimens as actually taken (effectiveness), the above analysis will be repeated including observed FEV₁ data over 12 weeks, for patients who completed the 12-week treatment period, including clinically and physiologically implausible data at week 12, and for patients who discontinued from treatment earlier than 12 week but from whom the sponsor was able to collect data post discontinuation. The sensitivity analysis will be conducted for both primary efficacy endpoints.

APPENDIX B. SENSITIVITY ANALYSIS: TIPPING POINT ANALYSIS

The following represents an outline of the planned methodology for the “tipping point” multiple imputation sensitivity analysis of the change from baseline in weekly average of the percent predicted trough morning FEV₁ at week 12. Minor deviations from this outline will be addressed in the CSR. In the situation that more significant updates are warranted, changes will be addressed in a SAP amendment to be finalized prior to database lock.

The tipping point analysis evaluates several combinations of imputed missing data values until it reaches a “tipping point” or point at which a particular combination of imputed missing data changes the study conclusions, as summarized by its p-value. This is a sensitivity analysis utilizing MI under the missing not at random (MNAR) assumption, and will only be conducted if a significant result ($p \leq 0.05$) is observed as part of the primary analysis. If the sensitivity analysis reveals that the tipping point consists of unreasonable values, then the robustness of the study results is supported.

Change from Baseline in Weekly Average of the Percent Predicted Trough Morning FEV₁ at Week 12:

In the tipping point analysis, missing percent predicted FEV₁ values will be imputed for patients who discontinued treatment before the week 12 visit for weekly average in which FEV₁ values are missing. MI and associated combining rules will be applied to propagate imputation uncertainty. In the placebo group, the missing percent predicted FEV₁ values will be imputed based on measurements observed at previous weeks and treatment group; that is, the missing data in the placebo group are assumed missing at random (MAR). For the active treatment groups, missing FEV₁ values will be imputed in the same manner, but then a constant (positive value) shift will be subtracted from the imputed FEV₁ values. The initial shift value will be zero (representing MAR) and it will then be increased and the process repeated until the treatment effect is no longer significant at the 5% level. The shift point at which the effect is no longer significant is the tipping point.

More specifically, the "tipping point" analysis will be performed using the following steps:

1. Assume patients with arbitrary missing data patterns, the fully conditional specification statement will be used to impute by using regression with treatment arm and percent predicted FEV₁ measurements from previous weeks as explanatory variables. For the 3 active treatment groups, MNAR will be assumed using specified shift parameters to adjust imputed values. For the placebo group, the imputed values will be generated using a zero shift parameter (namely, MAR is assumed for placebo). This will be done using code similar to the following:

```
proc mi data= outmi_mono seed=56789 nimpute=10 out=outmi;
  class trt sex therapy center;
  fcs nbiter=50 reg(wk1= &covlist trt / details);
  fcs nbiter=50 reg(wk2= &covlist trt wk1 / details);
  fcs nbiter=50 reg(wk3= &covlist trt wk1 wk2 / details);
```

```
fcs nbiter=50 reg(wk4= &covlist trt wk1 wk2 wk3 / details);
fcs nbiter=50 reg(wk5= &covlist trt wk1 wk2 wk3 wk4 / details);
fcs nbiter=50 reg(wk6= &covlist trt wk1 wk2 wk3
                  wk4 wk5 /details);
fcs nbiter=50 reg(wk7= &covlist trt wk1 wk2 wk3
                  wk4 wk5 wk6 / details);
fcs nbiter=50 reg(wk8= &covlist trt wk1 wk2 wk3
                  wk4 wk5 wk6 wk7 / details);
fcs nbiter=50 reg(wk9= &covlist trt wk1 wk2 wk3
                  wk4 wk5 wk6 wk7 wk8 / details);
fcs nbiter=50 reg(wk10= &covlist trt wk1 wk2 wk3
                  wk4 wk5 wk6 wk7 wk8 wk9 / details);
fcs nbiter=50 reg(wk11= &covlist trt wk1 wk2 wk3
                  wk4 wk5 wk6 wk7 wk8 wk9 wk10 / details);
fcs nbiter=50 reg(wk12= &covlist trt wk1 wk2 wk3
                  wk4 wk5 wk6 wk7 wk8 wk9 wk10 wk11 / details);

mnar adjust( wk1 / shift=&sj adjustobs=(trt='A' ));
mnar adjust( wk2 / shift=&sj adjustobs=(trt='A' ));
mnar adjust( wk3 / shift=&sj adjustobs=(trt='A' ));
mnar adjust( wk4 / shift=&sj adjustobs=(trt='A' ));
mnar adjust( wk5 / shift=&sj adjustobs=(trt='A' ));
mnar adjust( wk6 / shift=&sj adjustobs=(trt='A' ));
mnar adjust( wk7 / shift=&sj adjustobs=(trt='A' ));
mnar adjust( wk8 / shift=&sj adjustobs=(trt='A' ));
mnar adjust( wk9 / shift=&sj adjustobs=(trt='A' ));
mnar adjust( wk10 / shift=&sj adjustobs=(trt='A' ));
mnar adjust( wk11 / shift=&sj adjustobs=(trt='A' ));
mnar adjust( wk12 / shift=&sj adjustobs=(trt='A' ));

mnar adjust( wk1 / shift=&sj adjustobs=(trt='B' ));
mnar adjust( wk2 / shift=&sj adjustobs=(trt='B' ));
```

```
mnar adjust( wk3 / shift=&sj adjustobs=(trt='B' ) );
mnar adjust( wk4 / shift=&sj adjustobs=(trt='B' ) );
mnar adjust( wk5 / shift=&sj adjustobs=(trt='B' ) );
mnar adjust( wk6 / shift=&sj adjustobs=(trt='B' ) );
mnar adjust( wk7 / shift=&sj adjustobs=(trt='B' ) );
mnar adjust( wk8 / shift=&sj adjustobs=(trt='B' ) );
mnar adjust( wk9 / shift=&sj adjustobs=(trt='B' ) );
mnar adjust( wk10 / shift=&sj adjustobs=(trt='B' ) );
mnar adjust( wk11 / shift=&sj adjustobs=(trt='B' ) );
mnar adjust( wk12 / shift=&sj adjustobs=(trt='B' ) );

mnar adjust( wk1 / shift=&sj adjustobs=(trt='C' ) );
mnar adjust( wk2 / shift=&sj adjustobs=(trt='C' ) );
mnar adjust( wk3 / shift=&sj adjustobs=(trt='C' ) );
mnar adjust( wk4 / shift=&sj adjustobs=(trt='C' ) );
mnar adjust( wk5 / shift=&sj adjustobs=(trt='C' ) );
mnar adjust( wk6 / shift=&sj adjustobs=(trt='C' ) );
mnar adjust( wk7 / shift=&sj adjustobs=(trt='C' ) );
mnar adjust( wk8 / shift=&sj adjustobs=(trt='C' ) );
mnar adjust( wk9 / shift=&sj adjustobs=(trt='C' ) );
mnar adjust( wk10 / shift=&sj adjustobs=(trt='C' ) );
mnar adjust( wk11 / shift=&sj adjustobs=(trt='C' ) );
mnar adjust( wk12 / shift=&sj adjustobs=(trt='C' ) );
```

```
var trt &covlist wk1 - wk12;
```

```
run;
```

where: the order of &covlist includes: sex, (pool) investigational center, previous therapy, base, and age

Note: wk1 - wk12 is the AVAL raw data, change from baseline values should not be used in PROC MI procedure.

The same shift will be assumed for all weekly average and all active treatments.

2. The MMRM model will be fitted to the completed datasets using the model that was used for analysis. The difference will be estimated in adjusted LS means and p-value. SAS code similar to the following will be used:

```
ods output diffs=midiffs;
proc mixed data=dateset;
  by shift;
  class usubjid sex center therapy visit trt;
  model chg=base sex age center therapy visit trt visit*trt /
    ddfm=KR alpha=0.05;
  repeated visit / type=un sub=usubjid(trt) r;
    ** repeated visit / type=cs sub=usubjid(trt) r;
    ** if type=un fails to converge;
  lsmeans trt / diff cl;
run;
```

3. The results from the MMRM models will be combined using the following code:

```
data diffdt;
  set midiffs;
  comparison=trt||' vs '||left(_trt);
run;
proc sort data=diffdt;
  by comparison shift;
run;
ods output parameterestimates=miparm1;
proc mianalyze data=diffdt alpha=0.05 theta0=0;
  by comparison shift;
  modeleffects estimate;
  stderr stderr;
run;
```

4. Steps 2 through 3 will be repeated using different values for the shift parameter. After this step, for each shift parameter, a treatment effect (difference in adjusted means from placebo) and associated p-value will be estimated.

Since the tipping point analysis is to find out how much of a change is required to “tip” the result from statistically significant to not statistically significant, it will not be performed for any comparison that is not statistically significant at the onset.

Change from Baseline in 1-hour Postdose Percent Predicted Morning FEV₁ at Week 12:

The 1-hour postdose percent predicted morning FEV₁ measurement will be performed at the investigational center at the RV, TV2 (week 1), TV3 (week 2), TV4 (week 4), TV5 (week 8) and TV6 (week 12). MI method will be applied similarly to impute the 1-hour postdose missing data that are caused by early dropouts, then tipping point analysis will be performed.

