6.2.2.3. Sensitivity Analyses

The following list of sensitivity analyses are prespecified for this study, to evaluate alternative estimands and assess the robustness of the primary efficacy results. Each sensitivity analysis will be conducted for the 2 primary efficacy endpoints, unless otherwise noted.

- Effectiveness with retrieved dropout data: to evaluate the estimand of the effect of the treatment regimens as actually taken (effectiveness), the analysis will be repeated including observed FEV₁ data over 12 weeks, for patients who completed the 12-week treatment period and for patients who discontinued from treatment earlier than week 12 but from whom the sponsor was able to collect efficacy data post discontinuation. Early withdrawal patients for whom the sponsor fails to retrieve data post discontinuation despite all attempts to contact the patient, a reference-based

imputation (RBI), which is an MNAR mechanism, will be utilized. The RBI method multiply imputes the missing data in every treatment group based on an imputation model built using data from the placebo group. This will yield a conservative treatment effect estimate as compared to the estimate obtained from multiple imputations (MI) under MAR (see [Appendix A](#) for details).

- **Treatment completer analysis:** In this completer analysis, the estimand is conditional on taking IMP. This estimand applies to all patients in the ITT analysis set who have completed the 12-week treatment period; patients who have taken their medication as directed without any major protocol violations. Note that since the use of incorrect IMP is considered a major treatment administration protocol violation, “as randomized” will coincide with “as treated” for the treatment assignment in this population. No imputation will be used since this is a completer analysis.

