- **“Tipping point” multiple imputations:** similar to the primary estimand (change due to the initially randomized treatments as actually taken without retrieved dropout data), this sensitivity analysis will utilize multiple imputations under the MNAR assumption. For placebo patients, MAR will be assumed in all applications of multiple imputations. For the active arms, in the first application, MAR will be assumed and the imputations will be drawn from data in the corresponding active arms. In subsequent applications, shifts to the distribution of the active arms will be applied to represent different degrees of effect loss, ie, MNAR will be assumed. In this analysis, only data collected before IMP discontinuation will be utilized. If the sensitivity analysis reveals that the tipping point consists of unreasonable values, the robustness of the study results is supported. The methodology and algorithm used for imputations is provided in [Appendix B](#).
- **“2-dimensional tipping point” multiple imputations:** similar to above, the shifts to the distribution will apply to both placebo and active arms, to represent different degrees of effect loss. In this analysis, only data collected before IMP discontinuation will be utilized. An example below shows that a specified amount from actives will be subtracted from its value and at the same time, another specified amount will be added to the placebo. The methodology and algorithm used for imputations is provided in [Appendix C](#).

Table 6: An example of shift amount in percent predicted FEV₁

Placebo	Active
0	0
0	-5
0	-10
0	-15
2	-5
2	-10
2	-15

Placebo	Active
4	-5
4	-10
4	-15

Table 6: An example of shift amount in percent predicted FEV₁ (Continued)

Placebo	Active
6	-5
6	-10
6	-15

- Mixed approach of LOCF and baseline observation carried forward (BOCF): this sensitivity analysis will penalize discontinued patients who have a positive change from baseline score to zero by using (BOCF) method, thus these discontinued patients are treated as failures. While patients who discontinue IMP who have a negative change from baseline score will not have their results adjusted (LOCF) since their scores are already poor. In this imputation method, the imputed value is the lower between LOCF and BOCF for each patient. No adjustments will be made to the results for patients who complete the study. Retrieved dropout data will be included for this analysis. Details are provided in [Appendix D](#).

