7. MULTIPLE COMPARISONS AND MULTIPLICITY

7.1. Multiple Comparisons for the Primary Analysis

For the analysis of the co-primary endpoints, a fixed-sequence multiple testing procedure will be employed to control the overall Type I error rate at the 0.05 level, as described in [Table 7](#). Specifically, treatment comparisons will begin with the first primary endpoint, [1] 1-hour postdose percent predicted morning FEV₁ at week 12 at the FS MDPI 50/12.5 versus Fp MDPI 50 mcg. If the resulting p-value is less than 0.05, then the next comparison of interest will be made, according to the direction of the arrow. This process will continue until the point where the p-value is greater than 0.05 at which no further comparisons will be interpreted inferentially.

Taking into consideration that this is the very first study that utilizes the handheld device in a large Phase 3 study in a pediatric asthma patient population (4 through 11 years of age), an unplanned blinded sample size re-assessment was conducted. Since the adjustment to sample size was based on blinded standard deviation, no adjustment to the multiplicity control is warranted.

No multiplicity adjustment will be made for sensitivity analyses of the primary endpoints or subgroups.

Table 7: Multiple Testing Procedures

Sequence	Primary Endpoint	Hypothesis Testing
1	[1] Change from baseline in 1-hour postdose percent predicted morning FEV ₁ at week 12	FS MDPI 50/12.5 mcg BID vs. Fp MDPI 50 mcg BID
		↓
2	[2] Change from baseline in weekly average of the percent predicted trough morning FEV ₁ at week 12	Fp MDPI 50 mcg BID vs. Placebo
		↓
3	[2] Change from baseline in weekly average of the percent predicted trough morning FEV ₁ at week 12	Fp MDPI 25 mcg BID vs. Placebo

FEV₁= forced expiratory volume in 1 second; FS MDPI = fluticasone propionate/salmeterol xinafoate multidose dry powder inhaler, Fp MDPI = fluticasone propionate multidose dry powder inhaler.

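### As written, the tipping-point analysis shifts FS and Fp 50 by the same amount, so it hardly tests the first confirmatory comparison, and its code reads a visit average, not week 12

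*SAP*

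**What the plan says.** **Scope.** Section 6.2.2.3 says "Each sensitivity analysis will be conducted for the 2 primary efficacy endpoints, unless otherwise noted". The 1-hour paragraphs that close Appendices B and C confirm that the tipping-point analyses cover that endpoint.

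**First test.** Table 7 in Section 7.1 puts "FS MDPI 50/12.5 mcg BID vs. Fp MDPI 50 mcg BID" first in the fixed sequence, on the 1-hour endpoint. The trough comparisons with placebo come after it.

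**Shift rule.** Appendix B gives arms A, B and C the same macro value `&sj` at every week and states: "The same shift will be assumed for all weekly average and all active treatments". Appendix C keeps this for the active arms and, as Section 6.2.2.3 explains, "another specified amount will be added to the placebo". Table 6 has a single column for active treatment. For the 1-hour endpoint both appendices say only that the imputation is done in a similar way and that the tipping-point analysis follows. Step 4 of Appendix B describes the output as a difference from placebo.

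**Interpretation.** Section 6.2.2.3: "If the sensitivity analysis reveals that the tipping point consists of unreasonable values, the robustness of the study results is supported".

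**Model.** Step 2 of Appendix B: "The MMRM model will be fitted to the completed datasets using the model that was used for analysis". The code below it fits a repeated-measures model over all visits and requests `lsmeans trt / diff cl`. The primary analysis in Appendix A is an ANCOVA whose code keeps only week 12.

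**The concern.** A tipping-point analysis is informative only if its shifts work against the claim being tested. For the trough endpoint the comparator is placebo, so lowering all active arms together does that. For FS versus Fp 50 both arms are active. Lowering both by the same amount leaves their difference almost where it was, and a placebo shift does not enter the contrast at all. A large tipping point would then follow largely from the construction, whatever the FS dropouts look like, and the SAP's rule would count it as support. This matters most for the first test, because every later confirmatory claim depends on it.

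The second issue is separate. If the tipping code estimates a difference averaged over visits, the shift that it reports does not refer to the week-12 result that it is meant to stress.

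**Working it through.** **Inputs.** From SAP Section 2.4: SD 22, the figure 6.5, two-sided 5%, 80% power, 181 evaluable and 206 randomized per arm, 12% dropout overall. The SAP calls 6.5 an overall mean change. It is used here as a treatment difference because that reproduces the plan's sample size:

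- n per arm = 2 × (1.960 + 0.842)² × 22² / 6.5² ≈ 180 by the normal formula, and 181 by the t-test; 181 / 0.88 ≈ 206.

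Missingness by arm is not in the documents, so it is assumed and varied.

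**Effect of a shift.** Lowering the imputed values of a fraction m of an arm by s moves the arm mean by −m·s and adds m(1−m)s² to its variance. For an observed difference D in FS minus Fp 50:

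- d = D − m_FS·s_FS + m_Fp·s_Fp
- SE = √{[2·22² + m_FS(1−m_FS)s_FS² + m_Fp(1−m_Fp)s_Fp²] / 206}, which is 22·√(2/206) = 2.168 with no shift

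With one common shift s, d = D − s(m_FS − m_Fp). At equal missingness d = D, and only the growing SE can end significance.

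**Tipping points** (d/SE = 1.96, equal missingness):

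| D | Missing per arm | Common shift | FS only |
|---|---|---|---|
| 6.5 | 6% | 107 | 35 |
| 6.5 | 12% | 78 | 18 |
| 6.5 | 18% | 66 | 12 |
| 5.0 | 12% | 42 | 6 |

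For the common shift in row 2: (6.5/1.96)² × 206/2 − 484 ≈ 649; 649 / (0.12 × 0.88) ≈ 6,144; the square root is 78.4. With 181 in place of 206 throughout, the same steps give about 70 (common) and 16 (FS only).

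**p-values at 12% missing:**

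| Shift | D = 6.5, common | D = 6.5, FS only | D = 5.0, FS only |
|---|---|---|---|
| 5 | 0.0028 | 0.0066 | 0.043 |
| 10 | 0.0030 | 0.015 | 0.081 |
| 15 | 0.0034 | 0.032 | 0.145 |

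At D = 5.0 the unshifted p is 0.021. A common shift of 15, the largest active shift in Table 6, gives 0.024.

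**Unequal missingness, common shift 15, D = 6.5.** With 8% missing in FS and 12% in Fp 50: 6.5 − 1.2 + 1.8 = 7.1, in favour of FS. With 12% and 8%: 6.5 − 1.8 + 1.2 = 5.9, against 4.7 if FS alone is shifted.

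**How often the two schemes disagree.** At 12% missing, the smallest observed difference that stays significant is 4.25 unshifted, 1.96 × 2.220 = 4.35 with a common 15, and 1.96 × 2.194 + 1.8 = 6.10 with FS alone at 15. If the true difference is 6.5, then 31% of trials significant at zero shift pass the common 15 and fail the FS-only 15. The range is 14% to 51% for 6% to 18% missing, with SE on 206. A simulation of 3,000 four-arm trials with multiple imputation at 12% missing gave 33%: 98.9% stayed significant at the common 15 and 66.0% at the FS-only 15.

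**Week 12 versus visit average.** In a model with a visit-by-treatment term, `lsmeans trt` averages over visits. Appendix E uses the same model form and describes its result as a time-averaged difference. Suppose dropout builds up linearly to week 12. The shift then carries 78/144 = 54% of its week-12 weight over 12 weekly visits, and 27/60 = 45% over the 1-hour visits at weeks 1, 2, 4, 8 and 12. The net direction is not fixed: dilution overstates robustness if the effect is steady over time, but need not if the effect grows.

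**The case against.** **The appendices are outlines written for the trough endpoint.** The common-shift sentence sits under that heading, and the code is offered as an example. Appendix A's code also compares only with placebo, and nobody concludes from this that FS versus Fp 50 goes untested. So one could say that the 1-hour scheme is merely unspecified. Part of this stands: another scheme may be intended. But Section 6.2.2.3 itself describes shifting the active arms and covers both endpoints, and no alternative is written anywhere. A programmer following the text would apply the common shift.

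**The primary analysis already penalises FS.** It states "For all patients who prematurely discontinue from IMP, regardless of assigned treatment arm, imputation will be based on data from the placebo-treated patients", which removes up to 0.12 × 6.5 = 0.78 points, the same as an FS-only shift of 6.5. The retrieved-dropout, completer and LOCF/BOCF analyses also cover this endpoint. That is true, but each is one scenario. Only the tipping-point analyses are graded.

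**The frequency figure uses a lenient gate.** Appendix B runs the analysis only after a significant primary result, and the primary analysis is placebo-based. Requiring 0.88 × D to reach 4.25 (D at least 4.83) lowers 31% to about 27%. On the same basis the 5.0 example becomes 4.4, with p = 0.042 using SE 2.168 or 0.057 using 2.313 (181 per arm). In the latter case no tipping analysis would be run. These are fair qualifications and do not change the conclusion.

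**A shift of 15 is not a pass mark.** Table 6 is an example, and 15 points on FS alone is more than twice the assumed effect. This stands. The comparison shows how differently the two schemes behave and sets no threshold.

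**Conclusion.** The concern holds. Under the only scheme written, the tipping-point analysis does not deliberately penalise FS relative to Fp 50. The cancellation is exact at equal missingness. If FS loses more patients there is a small incidental penalty; if it loses fewer, the shift helps FS. In the illustration the common shift inflates the tipping point from about 18 to about 78 points at a difference of 6.5 and 12% missing. Roughly 27% to 33% of significant trials would look robust to a 15-point shift under the common scheme only.

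These sizes rest on assumed by-arm missingness, on 6.5 as a treatment difference, and on one shift per missing value. They ignore any build-up of shifts through the sequential weekly regressions, which would change the nominal tipping points.

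The second point also holds: the text and headings promise week 12, and the code delivers an average over visits. Its effect on the tipping point cannot be sized from the documents.

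Only sensitivity analyses are affected. Primary p-values and Type I error are not. The change should be made, but it does not threaten the primary result.

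**What to change.** 1. State a shift scheme for the 1-hour endpoint. In Appendix B, hold Fp 50 (arm B) at missing at random and shift FS (arm C) alone. In Appendix C, use a grid with independent shifts for FS and Fp 50.
2. Reword step 4 to name FS minus Fp 50 for this endpoint. The existing `lsmeans trt / diff` request, processed by comparison, already outputs that pair.
3. For both endpoints, fit the primary week-12 ANCOVA to each imputed dataset and combine the estimates. Alternatively, take the week-12 visit-by-treatment LS-mean difference from the repeated-measures model.
4. Editorially, correct the Appendix C sentence that gives every treatment group the same shift, since that appendix varies placebo separately.

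The cost is a few lines of SAP text and code before database lock and slightly more computation. No new data are needed.
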